- The secondary analyses will not be adjusted for multiple testing; however, the results of all statistical testing will be reported according to the American Statistical Association guidelines to provide the necessary context for interpretation.¹⁷
- All estimates of treatment effect will be accompanied by 95% confidence intervals (CI).
- All analyses will be performed using the R software package (R Core Team, 2008; www.R-project.org).

Interim analyses and the Data Safety Monitoring Board

An independent DSMB will review unblinded data to examine recruitment rate, patient characteristics, randomisation compliance, treatment compliance, completeness of data, outcomes and adverse events on three occasions (following the completion of 90-day follow-up for the 716th, 1432nd and 2150th patient, respectively). The DSMB charter is available at: <https://www.ualberta.ca/critical-care/research/current-research/starrtaki/documents.10>

Analysed datasets

All main analyses will be performed on the ITT population dataset. For these analyses, all patients will be analysed according to the group to which they were randomised; however, any randomised patient found to have not fulfilled eligibility criteria based on data available at the time of initial assessment (ie, randomised in

error) will be excluded following independent adjudication by two investigators who will be blinded to outcomes.¹⁸

Trial profile

The flow of patients through the trial will be shown in a Consolidated Standards of Reporting Trials (CONSORT) diagram (Figure 1).¹⁹ The figure will provide a summary of the number of patients screened, the number of patients who fulfilled eligibility, the number of patients who were excluded and the reason(s) for exclusion.

Patient characteristics and baseline comparisons

- A description of baseline characteristics will be presented by treatment allocation, as outlined in the proposed Table 1 .
- Categorical variables will be summarised with frequencies and percentages. Percentages will be calculated according to the number of patients for whom data are available.

- Continuous variables will be summarised as means with standard deviation (SD) or medians with the interquartile range (IQR) (Q1 and Q3).

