- Baseline measures for all patients will be tabulated for the following variables: ▶ sociodemographics; ▶ admission characteristics; ▶ pre-existing comorbidities; ▶ primary diagnostic category; ▶ vital signs at the time of randomisation; ▶ laboratory data at the time of randomisation; ▶ baseline kidney function; ▶ severity of illness at the time of randomisation; and ▶ organ support (eg, mechanical ventilation, vasopressor therapy) at the time of randomisation.

The information on the proposed additional figures and supplementary tables and figures is included in the online Appendix (available at cicm.org.au/Resources/Publications/Journal).

Analysis of adherence to timelines for randomisation and renal replacement therapy initiation

Compliance with randomisation will be reported and defined as the proportion of all enrolled patients who are randomised within 12 hours of fulfilling eligibility. Compliance with treatment allocation will also be reported overall and separately for both the accelerated and standard groups. In the accelerated group, compliance will be defined as the proportion of patients initiating RRT within 12 hours of meeting all eligibility criteria. In the standard group, compliance will be defined as the proportion of patients who initiated RRT more than 12 hours from the time of eligibility or who did not receive RRT at any time during the follow-up period.

Protocol deviations

Protocol deviations will be summarised as the number of deviations by type (eg, randomisation of ineligible patient, failure to adhere to randomisation timeline, failure to adhere to allocated intervention). All deviations will be listed and will be adjudicated by the principal investigators

Table 1. Baseline characteristics by treatment allocation*

Characteristic	Accelerated strategy	Standard strategy
	(N = xxxx)	(N = xxxx)
Age (years), mean (SD)	xx.x ± x.x	xx.x ± x.x
Female sex, n (%/0)	xxxx (xx.x%)	xxxx (xx.x%)
Weight (kg), mean (SD)	xx.x ± x.x	xx.x ± x.x
Coexisting conditions, n (%/0)		
Hypertension	xxxx (xx.x%)	xxxx (xx.x%)
Diabetes mellitus	xxxx (xx.x%)	xxxx (xx.x%)
Heart failure	xxxx (xx.x%)	xxxx (xx.x%)
Coronary artery disease	xxxx (xx.x%)	xxxx (xx.x%)
Liver disease	xxxx (xx.x%)	xxxx (xx.x%)
Metastatic cancer	xxxx (xx.x%)	xxxx (xx.x%)
Hematologic malignancy	xxxx (xx.x%)	xxxx (xx.x%)
AIDS	xxxx (xx.x%)	xxxx (xx.x%)
SAPS II score at enrolment, † mean (SD) xx.x ± x.x	xx.x ± x.x	SOFA score at enrolment, † mean (SD) xx.x ± x.x
Admission type, n (%/0)		

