Scheduled surgery	(xx.x%)	xxxx (xx.x%)
Unscheduled surgery (xx.x%)	xxxx (xx.x%)	Medical xxxx (xx.x%)
Hospital-acquired risk factors for AKI in preceding 7 days, n (%/0)		
Cardiopulmonary bypass	xxxx (xx.x%)	xxxx (xx.x%)
Aortic aneurysm repair	xxxx (xx.x%)	xxxx (xx.x%)
Other vascular surgery	XXXX (xx.x%)	xxxx (xx.x%)
Major trauma	xxxx (xx.x%)	xxxx (xx.x%)
Obstetric complications	xxxx (xx.x%)	xxxx (xx.x%)
Radiocontrast exposure	XXXX (xx.x%)	xxxx (xx.x%)
Receipt of aminoglycosides	xxxx (xx.x%)	xxxx (xx.x%)
Receipt of amphotericin B	xxxx (xx.x%)	xxxx (xx.x%)
Sepsis, n (%/0) xxxx (xx.x%)	xxxx (xx.x%)	Septic shock, n (%/0) xxxx (xx.x%)
Physiological support, n (%/0)		
Mechanical ventilation	xxxx (xx.x%)	xxxx (xx.x%)
Vasoactive support	xxxx (xx.x%)	xxxx (xx.x%)

Serum creatinine, baseline (mg/dL), mean (SD) xxx.x ± x.x xxx.x ± x.x eGFR (ml-/min/l .73m²), mean (SD) xxx.x ± x.x xxx.x ± x.x

Serum creatinine, randomisation (mg/dL), mean (SD)	xxx.x ± x.x	± X.X
Patients with oliguria or anuria, n ^(/0)	xxx (xx.x%)	xxx (xx.x%)
Urine output (ml-]24 h), mean(SD)	xx.x ± x.x	xx.x ± x.x
Blood urea nitrogen (mg/dL), mean (SD)	xx.x ± x.x	xx.x ± x.x
Serum potassium (mmol/L), mean (SD)	x.x ± x.x	x.x ± x.x
Serum bicarbonate (mmol/L), mean (SD)	xx.x ± x.x	xx.x ± x.x

xx.x ± x.x

xx.x ± x.x

AIDS = acquired immunodeficiency syndrome; AKI = acute kidney injury; SAPS = Simplified Acute Physiology Score; SOFA = Sequential Organ Failure Assessment; eGFR = estimated glomerular filtration rate. * Plus—minus values will be expressed as mean ± standard deviation (SD) (where the distribution of the data are not normal, median [interquartile range] will be reported instead of mean ± SD). t Scores on the SAPS II range from 0 to 163, with higher scores indicating more severe disease and a higher risk of death. Scores on the SOFA score range from 0 to 24, with higher scores indicating more severe disease and a higher risk of death.

to classify as to whether they were potentially avoidable, with disagreements resolved by discussion. Analysis of the primary outcome

Principal analysis

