The number and percentage of deaths through 90 days after randomisation will be reported for each treatment group. The primary effect estimate will be the relative risk of 90-day mortality, reported with 95% CI. The absolute risk difference and 95% CI will also be reported. Deaths up to 90 days after randomisation will be compared between the treatment groups using test. Additionally, the odds ratio (OR) (95% CI) will also be determined, primarily to permit comparisons between the primary unadjusted analysis and the various secondary pre-specified adjusted analyses of 90day mortality (Table 2).

Adjusted sensitivity analysis

Death at 90 days will also be analysed, adjusting for baseline characteristics (eg, age, sex, baseline eGFR, Simplified Acute Physiology Score [SAPS] II score at randomisation, surgical status, and presence of sepsis). Continuous variables (eg, age, eGFR and SAPS II score) will be modelled using restricted cubic splines with four knots to accommodate the possibility of non-linear relationships with the log odds of death. The OR and 95% CI will be determined first, primarily to permit comparisons between the unadjusted analysis and the secondary adjusted analyses of 90-day mortality. The adjusted treatment effect will be reported as the adjusted OR (95% CD. Should the adjusted OR be materially different from the unadjusted OR, a second adjusted model will be fit that employs the log link to provide adjusted estimates of the risk ratio. An additional sensitivity analysis will include site as a random effect in a generalised linear mixed model to assess if the variance component is important and affects inference.

Treatment of missing data

If more than 5% of patients from the ITT population are excluded from the adjusted analysis of the primary outcome due to missing data for baseline covariates, missing data will be imputed using fully conditional specification ²⁰ The imputation model will include all covariates required for the adjusted analysis as well as other baseline variables deemed related to the variables for which imputations are required. The multiple imputation will then be performed via chained equations to obtain ten imputed datasets. The adjusted analysis will be performed on the imputed datasets with the results appropriately pooled.

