Evaluation of heterogeneity in treatment effect Death at 90 days will also be analysed across baseline predicted risk of death using the SAPS II score ²¹ This analysis will be assessed by adding an interaction between treatment and SAPS II in the fully adjusted model described earlier.

Subgroup analyses

We will evaluate the effect of allocated treatment on the primary outcome across the following a priori defined subgroups by means of interaction terms in the adjusted model and displayed in a forest plot: ● patient sex; ● baseline eGFR, ● baseline SAPS II score; ● primary reason for ICU admission surgical versus medical; ● sepsis; and ● geographic region (eg, North America, Europe, Australia/ New Zealand, Asia/South America etc).

Exploratory analyses of the primary outcome We will further evaluate the primary outcome with the following exploratory analyses:

- We will examine the effect of the allocated treatment on the primary endpoint in a per-protocol population, defined by omitting patients with a protocol violation due to crossover to the opposite allocated treatment to which they were randomised.

- We will examine the effect of the treatment on the primary endpoint in a modified ITT (mITT) population. The mITT population will be defined as an "as treated" population, whereby patients with a protocol violation will be analysed in the treatment arm that reflects the RRT initiation strategy that was received.
- To further inform the interpretability of the main primary analysis, we will examine the utility of a Bayesian analysis approach, across a range of plausible reference and data-driven priors, to provide estimates of the posterior probability of any mortality benefit (using both relative risk and absolute risk reduction), of an accelerated compared with standard strategy for RRT initiation in critically ill patients with severe AKI ²²
These proposed exploratory analyses may be reported after the publication of the main trial findings.

Additional analyses of mortality

The analysis of all-cause mortality described in the main analysis will be replicated to compare the proportion of patients who died in the ICU, before hospital discharge, and at 28 days after randomisation, respectively. No additional adjusted or subgroup analyses will be performed on these endpoints.

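### The imputation model leaves out 90-day death and treatment-by-death, so SAPS II and eGFR interactions fitted on imputed data would be pulled toward no heterogeneity

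*SAP*

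**What the plan says.** The SAP section on treatment of missing data sets a trigger that concerns the baseline covariates: "If more than 5% of patients from the ITT population are excluded from the adjusted analysis of the primary outcome due to missing data". Above that level, chained equations are run to give ten datasets. The section then lists what enters the imputation model: "The imputation model will include all covariates required for the adjusted analysis as well as other baseline variables deemed related to the variables" needing imputation. It continues: "The adjusted analysis will be performed on the imputed datasets with the results appropriately pooled".

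The adjusted model contains, as examples, age, sex, baseline eGFR, SAPS II, surgical status and sepsis, with four-knot splines for the continuous ones. Two of these are also effect modifiers. The heterogeneity section tests SAPS II by "adding an interaction between treatment and SAPS II in the fully adjusted model described earlier". The subgroup section examines eGFR, SAPS II and four other factors "by means of interaction terms in the adjusted model". Neither section says whether those models are fitted to the imputed datasets.

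The SAP allows for incomplete baseline data: "Percentages will be calculated according to the number of patients for whom data are available". Neither document gives an expected missing fraction for any covariate.

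**The concern.** Ninety-day death is neither a covariate nor a baseline variable, so an ordinary reading of the list leaves it out, and no other section adds it. Missing SAPS II or eGFR values are then drawn as if they carried no information about death beyond the other listed variables. In patients with imputed values, the link between covariate and death is diluted. So is any difference in that link between the arms, and that difference is the interaction.

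The stake is the reading of the heterogeneity analyses. If missingness does not depend on death given the covariates, complete cases estimate the interaction almost without bias. Crossing the 5% trigger would then replace that estimate with one biased toward no heterogeneity.

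**Working it through.** **Inputs.** From the documents: 40% control mortality and a 15% relative reduction (Protocol 2.9), hence 34% and a treatment log-OR of ln(0.34/0.66) − ln(0.40/0.60) = −0.26; at least 3,000 patients (SAP, Sample size); ten imputed datasets. Assumed, because the documents give none: missing fractions, covariate effects, interaction sizes and auxiliary correlations. The plan states no figure on this point that could be reproduced.

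**Step 1: large-sample limit, no auxiliary.** Let x be a standardised covariate missing completely at random with probability m, and let the risk in each arm be p(x) = expit(a + b·x), with a = −0.40 (standard) and −0.66 (accelerated). If x is imputed without death, the risk given the completed value x* is

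P(death | x*) = (1 − m)·p(x*) + m·p̄,

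where p̄ is the arm's mean risk. A logistic model is refitted in each arm; the interaction is the difference in slopes.

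- Weak predictor, m = 0.20: true slopes 0.30 and 0.45 become 0.2382 and 0.3543. Interaction 0.1161 against 0.15, a loss of 1 − 0.1161/0.15 = 22.6%.
- Strong predictor, m = 0.20: 0.70 and 1.00 become 0.5388 and 0.7451. Interaction 0.2063 against 0.30, a loss of 31.2%.
- No interaction, m = 0.20: 0.70 and 0.70 become 0.5388 and 0.5396. Difference 0.0008, so practically no bias.

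| Slope per SD, interaction | 5% missing | 10% | 20% | 30% |
|---|---|---|---|---|
| 0.3, 0.15 | 5.8% | 11.5% | 22.6% | 33.2% |
| 0.5, 0.15 | 6.9% | 13.4% | 25.6% | 36.8% |
| 0.7, 0.3 | 8.9% | 17.0% | 31.2% | 43.3% |

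**Step 2: trials of the planned size.** 3,000 patients, the six covariates above, one auxiliary baseline variable correlated 0.7 with the missing covariate, missing completely at random, normal-regression imputation, ten datasets, Rubin's rules. Allocated treatment is taken to be in the listed model. Loss of an eGFR interaction of 0.25 log-odds per SD, against full data (1,000 trials each):

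| Imputation model | 6% missing | 10% | 20% | 40% |
|---|---|---|---|---|
| As listed, no auxiliary | 5% | 8% | 17% | 33% |
| As listed, with auxiliary | 3% | 5% | 9% | 19% |
| Auxiliary plus death | 3% | 5% | 9% | 19% |
| Auxiliary plus death and treatment-by-death | 0.5% | 0.4% | 0.5% | 1.7% |

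Complete cases stay within about 1%. For SAPS II, simulated as a stronger predictor, the losses at 6% and 20% missing are 8% and 26% without the auxiliary, 4% and 14% with it, and 1% and 3% with auxiliary and product. Adding death alone does not repair the interaction; the product is needed.

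**Step 3: variations at 20% missing (eGFR).** Auxiliary correlations of 0.5, 0.7 and 0.9 give 13%, 9% and 4%. With missingness depending on age, SAPS II and surgery: 19% without auxiliary, 11% with it, 2% with the product. With four-knot splines for the continuous covariates: 17%, 10% and 2%.

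**Step 4: what does not move.** Adjusted treatment OR at 20% missing: 0.796 to 0.801 (SAPS II missing), 0.753 to 0.754 (eGFR missing). In the large-sample runs it went from 0.745 to 0.753 at 20% and from 0.746 to 0.760 at 40%. A null interaction at 20% was −0.007 as listed and −0.010 on full data (Monte Carlo SE 0.004). The inverse-probability-weighted log-OR for RRT dependence moved 0.003 at 20% and 0.007 at 40%, against a sampling SD of 0.18.

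**Step 5: total error.** RMSE for the eGFR interaction of 0.25, list with auxiliary / product with auxiliary / complete cases: 0.083 / 0.085 / 0.087 at 6%; 0.080 / 0.085 / 0.090 at 20%; 0.090 / 0.098 / 0.113 at 40%.

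**The case against.** The strongest reply is that little the trial will report is at risk. The text does not say that the list is exhaustive, and a competent analyst may add death anyway. The trigger counts patients missing any covariate, so a single modifier may be missing less often than 5%. Baseline creatinine for eligibility falls back to the lowest in-hospital value (Protocol 2.2.2); if baseline eGFR uses the same rule, few values may be missing. With the auxiliaries that the list allows, the bias at 6% missing is about 3% × 0.25 = 0.0075 log-odds against an RMSE of 0.083. An interaction of 0.25 per SD is itself large, close to the whole design effect of 0.26. Confidence-interval coverage under the list was 92–99%, and its RMSE is lower than that of the corrected model or of complete cases.

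Most of this stands, and it sets the severity. It does not remove the point. The SAP states a concrete list that omits the outcome, and a pre-specified rule should not rely on the analyst departing from it. The list's lower RMSE comes only from unplanned shrinkage toward no heterogeneity; if shrinkage is wanted, it should be chosen and stated.

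Four stronger readings are tempting but not supported:

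- That the primary result is biased. It is unadjusted and uses no imputed covariates.
- That the adjusted treatment effect is materially distorted. It hardly moves.
- That shrunken covariate coefficients are a harm in themselves. The SAP reports the adjusted treatment OR, and Table 2 has no rows for those coefficients.
- That baseline eGFR will be missing in many patients because Protocol 2.2.3 expects pre-hospital creatinine often to be unavailable. That remark concerns an exclusion criterion, and the fallback may cover the gap.

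**Conclusion.** The point holds as a conditional, low-severity one. Four things must coincide: the 5% trigger is met, the list is followed as written, the SAPS II and eGFR interaction models use the imputed data, and the true interaction is not zero. The third is an inference from the SAP's reference back to the adjusted model.

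Without an auxiliary variable, the interaction then shrinks by about the missing fraction for a weak predictor and by roughly 1.3 to 1.6 times it for a strong one such as SAPS II (26/20 = 1.3; 31.2/20 = 1.56). That is about 17–31% at 20% missing. With an auxiliary correlated 0.7 the loss is about half as large, and near the trigger it is about 3–9%.

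These sizes rest on assumed effects, correlations and missing fractions, and on an interaction summarised as one linear term per SD. The direction does not depend on the particular values tried. The affected analyses are secondary or exploratory, and for these the SAP avoids formal hypothesis testing.

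**What to change.** In the section on treatment of missing data, state that the imputation model includes 90-day death, allocated treatment and their product (or imputes within each arm with death included), together with the listed covariates and auxiliary baseline variables. In the heterogeneity and subgroup sections, state that the interaction models use those imputed datasets. It would also help to say which creatinine defines baseline eGFR and to report the missing fraction of each adjustment covariate.

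This removes most of the bias, not all. For a strong predictor at 20% missing, 3% remained for SAPS II in the trial-sized simulations. About 6% remained in a large-sample run without an auxiliary (slope 0.7, interaction 0.3), and 8% when missingness there depended on another covariate.

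The cost is two sentences, a changed imputation call and somewhat more variable interaction estimates. With the auxiliary, RMSE rises by 3–9% for an interaction of 0.25, and by up to 22% for one of 0.10 at 40% missing. Design, data collection and the primary test are unchanged.

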2.2.2 Inclusion criteria

All of these must be fulfilled at the time of screening assessment:

- 1- Age \geq 18 years (Operational definition: Patient's age on the day of eligibility screening.)
- 2- Admission to a critical care unit (Operational definition: Any unit where there is capability to administer invasive mechanical ventilation.)
- 3- Evidence of kidney dysfunction (Operational definition: serum creatinine \geq 100 $\mu\text{mol/L}$ [women] and \geq 130 $\mu\text{mol/L}$ [men] based on most recent bloodwork available prior to screening and that has not declined by $>$ 27 $\mu\text{mol/L}$ compared to the highest value recorded in the preceding 48 hours.)
- 4- Evidence of severe AKI based on at least one of the following three criteria:
 - i) \geq 2-fold increase in serum creatinine (sCr) from baseline (Operational definition: The baseline sCr is an *outpatient* reading within 365 days of the current admission date; if multiple pre-hospitalization values are available, the one closest to the date of hospital admission will be used. If an outpatient pre-hospitalization value is not available during the 365 days prior to admission date, the lowest creatinine value obtained during the current hospitalization should be taken as the baseline. This criterion is met if the current sCr is \geq 100% higher than the baseline value.)
 - ii) If current serum creatinine is \geq 354 $\mu\text{mol/L}$, this must be accompanied by evidence of a minimum increase of 27 $\mu\text{mol/L}$ from the baseline sCr. (Operational definition: If current sCr is \geq 354 $\mu\text{mol/L}$ and the patient has experienced an increase of 27 $\mu\text{mol/L}$ from the documented baseline, based on the definition delineated in i) for baseline sCr.)
 - iii) Urine output $<$ 6.0 mL/kg over the preceding 12 hours.

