2.2.3 Exclusion criteria

Any one of the criteria below would be grounds for exclusion:

- 1- Serum potassium concentration > 5.5 mmol/L (Operational definition: Based on last available bloodwork).
- 2- Serum bicarbonate concentration < 15 mmol/L (Operational definition: Based on last available bloodwork).
- 3- Presence of a drug overdose that necessitates initiation of RRT. (Operational definition: If noted in the chart or directly from the treating team as the primary reason for administering RRT.)
- 4- Lack of commitment to provide RRT as part of limitation of ongoing life support. (Operational definition: Critical care team has deemed the patient not to be eligible for escalation of life support, including the initiation of RRT, or substitute decision makers have declined offer of same.)
- 5- Any RRT within the previous 2 months. (Operational definition: If recorded in the medical chart by any clinician following the patient.)
- 6- Kidney transplant within the past 365 days. (Operational definition: As reflected in the medical chart.)
- 7- Known pre-hospitalization advanced chronic kidney disease, defined by an estimated glomerular filtration rate < 20 mL/min/1.73 m² in a patient who is not on chronic RRT. (Operational definition: The coordinator will review all documented serum creatinine values

within 365 days prior to the date of admission for the current hospitalization. The value closest to the admission date will be considered as the “baseline” and will be used to calculate the corresponding estimated glomerular filtration rate using an online calculator. A value of < 20 mL/min/1.73 m² derived from the CKD-EPI equation⁴² will be grounds for exclusion. The serum creatinine, age, sex, and race (Black/non-Black) is entered into a calculator found at: <http://www.qxmd.com/calculate-online/nephrology/ckd-epi-egfr>. It is expected that a large number of patients will not have readily available pre-hospitalization sCr data. In the case of a missing pre-hospitalization sCr, this exclusion criterion will be considered to have been NOT met.)

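### Ten imputed datasets is a fixed number that could leave avoidable random-seed noise in the exploratory treatment-by-eGFR interaction if baseline eGFR is often missing and imputed

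*SAP*

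**What the plan says.** **Imputation (SAP, Treatment of missing data).** The trigger is conditional and concerns missing baseline covariates: "If more than 5% of patients from the ITT population are excluded from the adjusted analysis of the primary outcome due to missing data". Once triggered, the number of datasets is fixed: "The multiple imputation will then be performed via chained equations to obtain ten imputed datasets". No seed and no criterion for Monte Carlo error are given. The content of the imputation model is described by covariates: "The imputation model will include all covariates required for the adjusted analysis as well as other baseline variables deemed related".

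**Where baseline eGFR enters.** The SAP's adjusted sensitivity analysis is described as "adjusting for baseline characteristics (eg, age, sex, baseline eGFR, Simplified Acute Physiology Score [SAPS] II score at randomisation, surgical status, and presence of sepsis", and continuous covariates "will be modelled using restricted cubic splines with four knots". Under Subgroup analyses, baseline eGFR is one of six factors assessed "by means of interaction terms in the adjusted model and displayed in a forest plot".

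**How much may be missing.** Protocol 2.2.3, exclusion criterion 7, bases the estimate of prior kidney function on creatinine from the year before admission and warns: "It is expected that a large number of patients will not have readily available pre-hospitalization sCr data". It gives no percentage. Protocol 2.2.2, criterion 4, defines baseline creatinine differently for the AKI criteria. With no outpatient value, "the lowest creatinine value obtained during the current hospitalization should be taken as the baseline". The SAP does not say which definition feeds its baseline eGFR, either in the text or in its Table 1.

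**Status of the result.** Under Analysis principles, the SAP treats secondary analyses as exploratory. P values are reported, but formal hypothesis testing is avoided.

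**The concern.** With multiple imputation, the pooled estimate and its P value vary with the random seed. The variation grows with the fraction of missing information (FMI) for the parameter and shrinks as imputations are added. For a treatment main effect in a randomized trial, missing covariate values cost almost no information. For an interaction with the incomplete covariate itself, the FMI can be a sizeable part of the missing fraction.

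A number fixed in advance at ten ignores this. If baseline eGFR were missing in a large share of patients and imputed, the same data and code could give visibly different P values for the eGFR interaction under different seeds. At stake is the reproducibility of one exploratory subgroup result. No decision about the trial's main question depends on it.

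**Working it through.** The plan gives no figure for imputation precision, so there is none to reproduce.

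**Inputs.** From the SAP: m = 10, the trigger of more than 5%, and an extended sample size of at least 3,000. From the protocol: 40% mortality in the standard arm. Assumed: the share of eGFR missing, the FMI, and the P value that unlimited imputations would give. The comparator m = 50 is the proposed change.

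**Step 1. From missing share to FMI.** A logistic simulation used 3,000 patients, about 40% mortality, eGFR missing at random, and other baseline variables explaining 25% of eGFR variance (assumed). It covered eGFR as a linear term and as a cut that puts about 23% of patients in the low group, with 12 datasets of 300 imputations per setting.

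| eGFR missing | FMI, interaction | FMI, treatment effect |
|---|---|---|
| 6% | 0.04–0.05 | below 0.001 |
| 20% | 0.13–0.16 | below 0.001 |
| 40% | 0.23–0.34 | below 0.001 |

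An FMI of 0.15 to 0.3 therefore stands for roughly 20% to 40% missing.

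**Step 2. Seed variation under Rubin's rules.** Scale the total variance at unlimited m to 1, so that the between-imputation variance is B = FMI and the within-imputation variance is W = 1 − FMI. Across seeds:

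- the pooled estimate has SD √(FMI/m);
- the estimated between-imputation variance is b = B·χ²(m−1)/(m−1);
- the total variance is T = W + (1 + 1/m)b;
- the reference t distribution has (m−1)(1 + 1/r)² degrees of freedom, with r = (1 + 1/m)b/W.

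The SD of the pooled estimate is:

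- FMI 0.15: √(0.15/10) = 0.122; √(0.15/50) = 0.055.
- FMI 0.3: √(0.3/10) = 0.173; √(0.3/50) = 0.077.

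**Step 3. Effect on a P value of 0.03.** This corresponds to z = 2.170. As a hand check for FMI 0.3 and m = 10, 2.170 ± 1.96 × 0.173 gives z from 1.83 to 2.51, that is P from 0.067 to 0.012. Adding the variation in b and the t reference by simulation (400,000 draws per setting) widens this to the range in the third row.

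| FMI | m = 10, central 95% of P | m = 50, central 95% of P | Two seeds on opposite sides of 0.05 (m = 10; m = 50) |
|---|---|---|---|
| 0.05 | 0.021–0.044 | 0.025–0.036 | under 1%; under 1% |
| 0.15 | 0.015–0.063 | 0.022–0.041 | 18%; under 1% |
| 0.3 | 0.010–0.094 | 0.018–0.050 | 37%; 4.5% |

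**Step 4. Limits of the gain.** For an underlying P of exactly 0.05 and FMI 0.3, the range is 0.018–0.134 at m = 10 and still 0.032–0.078 at m = 50. For an underlying P of 0.20 at the same FMI, almost no seed gives a value below 0.05, even with ten.

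The interaction of treatment with a four-knot spline, which has several degrees of freedom, was not simulated.

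**The case against.** **Heavy missingness is not established.** A reader might infer that the plan itself expects many baseline creatinines to be missing. The protocol's warning concerns pre-hospital values, for one exclusion criterion. Under the fallback in Protocol 2.2.2 nearly every patient has a baseline, because entry requires a recent creatinine. The trigger might then never be reached on account of eGFR. This objection stands, but it does not settle the matter. The section that describes calculating a prior eGFR (2.2.3) has no fallback, and the subgroup's rationale in Protocol 2.10 is pre-existing chronic kidney disease, which fits a pre-hospital value better. The source is simply undefined.

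**The link to the subgroup models is inferred.** The SAP ties imputation to the adjusted analysis and places the interactions in the adjusted model. It does not state that subgroup models are fitted to the imputed datasets. This stands as a condition of the point.

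**The result is exploratory.** No threshold applies to this P value, and confidence intervals accompany every estimate. This stands, and it limits the importance. It does not justify noise that can be removed at almost no cost.

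**A notable-or-not reversal is not the general case.** In a separate simulation, one dataset at 20% missing was re-imputed with 60 seeds. It gave P from 0.008 to 0.031 (5th to 95th percentile) with ten imputations, wholly below 0.05. A seed can move a result across a line mainly when the result lies near it.

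**Two statisticians.** A reader might also infer that the SAP's independent double analysis would be exposed. That requirement covers the primary outcome, whose principal comparison is unadjusted and needs no covariate imputation.

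**Conclusion.** The point holds conditionally and is minor. Ten imputations are fixed regardless of missingness. If baseline eGFR comes from pre-hospital creatinine, the trigger is met and the subgroup models use the imputed data, the eGFR interaction carries avoidable Monte Carlo noise. At an assumed FMI of 0.15 to 0.3, moving from ten to fifty imputations shrinks the width of the seed range around P = 0.03 from 0.048 to 0.019 (0.063 − 0.015; 0.041 − 0.022) at the lower end, and from 0.084 to 0.032 (0.094 − 0.010; 0.050 − 0.018) at the upper end.

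With about 5% missing, or with the in-hospital fallback as baseline, ten is adequate. The documents do not support the stronger reading that ten is too few as things stand, or that the trial's conclusions depend on the seed. The primary test uses no imputed covariates, and the FMI for the adjusted treatment effect is below 0.001 in every setting examined.

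**What to change.** In the SAP, under Treatment of missing data, replace ten with at least 50 imputed datasets, or one per percentage point of patients with any incomplete covariate if that is larger, and record the seed. The rule is safe under either definition of baseline eGFR, since extra imputations do no harm when little is missing. One added sentence could state which creatinine feeds baseline eGFR and whether the subgroup models use the imputed data; that would settle whether the point applies at all.

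The cost is a changed number and minor computing time. Trial conduct and the primary analysis are untouched.

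More imputations reduce seed dependence but do not remove it. Nor do they cure bias from an imputation model that omits the outcome or the interaction. The SAP's wording names neither, though it does not rule them out. In the simulation at 40% missing with a linear eGFR term, leaving them out gave an interaction coefficient of 0.077 against 0.135 with full data; including outcome, treatment and their product gave 0.105. That is a separate matter to specify in the same section.
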